## 9. STATISTICAL ISSUES

### 9.1. SAMPLE SIZE

The primary efficacy endpoint of the clinical trial will be the proportion of insulin-independent patients following IAT over the time frame: day 365±14 after the transplant.

In the following considerations, statistical significance for this endpoint will be achieved if the Pearson Chi-Square Statistic yields a two sided p-value less than 0.05. The corresponding false positive error rate is (one-sided) 0.025. In addition, 95% confidence interval for the difference of success (failure) rates between the reparixin and placebo groups will be provided, based on the normal distribution approximation to the standardized difference in estimated success rates.

Based on published data from a retrospective series (*Sutherland, 2012*), it appears that the likelihood of achieving insulin independence at 12 month follow-up in the placebo control arm depends upon the number of IEQ/kg, with patients categorized in three groups:

- < 2500 IEQ/kg: 13% insulin independence
- 2500-5000 IEQ/kg: 23% insulin independence
- > 5000 IEQ/kg: 55% insulin independence

In the overall series, the yields were <2500 IEQ/kg in 36%, 2500-5000 IEQ/kg in 39% and > 5000 IEQ/kg in 24% of patients. In the more recent series of 217 patients receiving IAT from 2006 to 2011, corresponding yields were <2500 IEQ/kg in 34%, 2500-5000 IEQ/kg in 42% and > 5000 IEQ/kg in 24%.

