##### **9.4.2. Primary and Secondary Endpoint analysis**

For the primary efficacy endpoint, the proportion of insulin-independent patients over the time frame of day 365 $\pm$ 14 after the transplant, the differences in proportions will be assessed using the Pearson Chi-square statistic, stratified by the three groups at baseline: < 2500 IEQ/kg vs. 2500-5000 IEQ/kg vs. > 5000 IEQ/kg. The significance level used for statistical testing will be 2.5% and one-sided test will be used. The 95% confidence interval for treatment proportions and for the difference in treatment proportion between reparixin and placebo will be produced. The primary analysis will be performed using both ITT population with PP analysis serving as a sensitivity analysis.

For secondary endpoints that will be tested both at 75 $\pm$ 14 and 365 $\pm$ 14 days after the transplant, only the day 365 $\pm$ 14 time point will be tested for superiority in the fixed sequence testing procedure.

The C-peptide AUC after the MMTT normalized by IEQ/kg will be analyzed at the two time points by a repeated measurements model using PROC MIXED within SAS®, including terms for treatment, time point and center. The treatment effect within each time point will be compared using a two-sided test at the 5% level. The estimated treatment difference between reparixin and placebo at each time point will be presented together with the corresponding 95% confidence interval. The confidence interval will be generated using  $\alpha=0.05$ .

The mean in average daily insulin requirements at the two time points will be analyzed using a repeated measurements model using PROC MIXED within SAS®. The model will include fixed effect

terms for center, time point and treatment. Time point will be specified as a repeated measurement. The treatment effect within each time point will be compared using a two sided test at the 5% level.

The proportion of patients with an HbA1c  $\leq 6.5\%$  will be analyzed at day  $365 \pm 14$ . Additionally, the proportion of patients with an HbA1c  $\leq 6.5\%$  at day  $365 \pm 14$  will be analyzed again, but patients are included in this second analysis if they are also free of severe hypoglycemic events from day  $75 \pm 14$  to day  $365 \pm 14$  inclusive. Treatment effect will be analyzed using Pearson Chi-square.

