### 1.2 Changes From Protocol

Not pertinent.

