### 3.3 Sample Size Considerations

The primary efficacy endpoint of the clinical trial is the proportion of insulin-independent patients following IAT at Day 365 ± 14 days after the transplant.

In the following considerations, statistical significance for this endpoint will be achieved if the Pearson Chi-square statistic yields a two sided p-value less than 0.05. The corresponding false positive error rate is (one-sided) 0.025. In addition, a 95% confidence interval for the difference of success (failure) rates between the reparixin and placebo groups will be provided based on the normal distribution approximation to the standardized difference in estimated success rates.

Based on published data from a retrospective series (Sutherland, 2012), it appears that the likelihood of achieving insulin independence at 12 month follow-up in the placebo control arm depends upon the number of IEQ/kg, with patients categorized in three groups:

- <2500 IEQ/kg: 13% insulin independence
- 2500-5000 IEQ/kg: 23% insulin independence
- >5000 IEQ/kg: 55% insulin independence

In their overall series, the yields were <2500 IEQ/kg in 36%, 2500-5000 IEQ/kg in 39% and >5000 IEQ/kg in 24% of patients. In the more recent series of 217 patients receiving IAT from 2006 to 2011, corresponding yields were <2500 IEQ/kg in 34%, 2500-5000 IEQ/kg in 42%, and >5000 IEQ/kg in 24%.

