Initial focus is placed on the cohort that is in the range 2500-5000 IEQ/kg, since these participants will be the largest fraction of enrollees. It is anticipated that the percentage of such patients achieving insulin independence will be increased from 23% in the placebo control arm to 55% in the reparixin arm. Using standard statistical formulas based on the approximation of the binomial distribution by the normal distribution, the sample size of 44 patients per arm provides 90% power to detect a 23% versus 55% true difference when using a Pearson Chi-square statistic having the traditional (one-sided) 2.5% false positive error rate. Even accounting for the discreteness, the power should be in the 87% to 90% range. Furthermore, with 44 patients per arm, statistical significance (i.e., one-sided  $p=0.025$ ) will be obtained if the estimated difference is 22.7% (10/44) versus 43.2% (19/44), which is an estimated 20.5% increase in percentage of patients achieving insulin independence. Hence, with 44 patients per arm, statistical significance is achieved with an estimated effect size that is clinically meaningful.

Even though the largest percentage of patients will be in the cohort receiving IEQ/kg in the range 2500-5000 IEQ/kg, the trial will also enroll participants in two additional strata: <2500 IEQ/kg and >5000 IEQ/kg. As noted above, we are presuming the middle strata would have an increase from 23% to 55% in percentage of patients achieving insulin independence. This is an odds ratio higher than 4. If we have an odds ratio of approximately 4.3 to 4.5 in the other 2 strata and if approximately 1/2 of the patients would be from the 2500-5000 IEQ/kg stratum, then only a modest increase of about 12 additional patients beyond the 88 patient sample size would be needed to maintain the statistical power of the trial. An increase in success rate from 13% to

REP0112

Statistical Analysis Plan

40% in the <2500 IEQ/kg stratum would be an odds ratio of 4.4 and an increase in success rate from 55% to 84% in the >5000 IEQ/kg stratum would be an odds ratio of 4.3.

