Based on these considerations, it is planned to enroll 100 patients in this trial who receive IAT, with the expectation that there will be approximately 5 others who do not receive IAT. Under such a plan, the trial would not be overpowered even if all participants were in the 2500-5000 IEQ/kg stratum since statistical significance (i.e., one-sided  $p=0.025$ ) would be obtained with 52 patients per arm if the estimated difference is 23.1% (12/52) versus 42.3% (22/52), which is an estimated clinically significant 19.2% increase in percentage of patients achieving insulin independence.

The sample size of 100 to 105 patients also provides high statistical power for the key secondary endpoint, C-peptide area under the curve (AUC) (mixed meal tolerance test [MMTT]) normalized by IEQ/kg. Based on preliminary data reported from the ongoing pilot trial, Month 1 post transplant means and standard deviations for this endpoint are  $1.92 \pm 1.62$  in the reparixin group and  $0.44 \pm 0.04$  in the control group. With 52 patients in each treatment group, the trial will have greater than 95% power to detect a difference in means of at least 1.48 (the difference between a treated mean of 1.92 and a control mean of 0.44) assuming that the common standard deviation is 1.37 and using an 0.0025 two-sided significance level.

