#### Primary Analysis

The proportion of insulin-independent patients will be compared between treatment groups using the Cochran-Mantel-Haenszel test stratified by baseline IEQ/kg (<2500 IEQ/kg, 2500-5000 IEQ/kg, and >5000 IEQ/kg). The hypothesis to be tested is:

Null Hypothesis,  $H_0$ :  $p_{\text{reparixin}} \leq p_{\text{placebo}}$  for all baseline IEQ/kg strata

Alternative Hypothesis,  $H_A$ :  $p_{\text{reparixin}} > p_{\text{placebo}}$  for at least one baseline IEQ/kg strata

The significance level used for statistical testing will be 2.5% and a one-sided test will be used. The 95% confidence interval for treatment proportions and the one-sided 95% confidence interval for the difference in treatment proportion between reparixin and placebo will be produced.

As a sensitivity analysis, the primary analysis will be repeated for the ITT population, dropping from the analysis any site with >20% of subjects not having data for the primary endpoint recorded; subjects will be considered to not have data recorded for the primary endpoint if they have discontinued the study prior to attending the Day 365 visit or if they have attended the Day 365 visit but did not have the primary endpoint recorded. The intent is to examine the sensitivity of the primary analysis to sites lacking a reasonable number of patients with data captured for the primary endpoint.

The relevance of the treatment-by-site interaction will be investigated using a logistic regression model which will include the main effect of treatment and IEQ/kg infused at IAT (<2500 IEQ/kg,

REP0112

Statistical Analysis Plan

2500-5000 IEQ/kg, and >5000 IEQ/kg) and site as covariates. The analysis variable for treatment will be coded such that the reference treatment is placebo, the analysis variables for IEQ/kg infused at IAT will be coded such that the reference group is <2500 IEQ/kg, and the analysis variables for site will be coded such that the reference site is Site 1. The treatment-by-site interaction will be examined, and if not significant at the 0.10  $\alpha$ -level, will be removed from the model. The hypothesis to be examined is:

Null Hypothesis,  $H_0$ :  $\beta_{\text{treatment}} \leq 0$

Alternative Hypothesis,  $H_A$ :  $\beta_{\text{treatment}} > 0$

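### The primary test is one-sided at 2.5%, but SAP 7.5.1 reports a one-sided 95% interval for the difference, so the interval can exclude zero when the test fails

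*SAP*

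**What the plan says.** SAP 7.5.1 (Primary Analysis) compares the arms with a Cochran-Mantel-Haenszel (CMH) test stratified by IEQ/kg: "The significance level used for statistical testing will be 2.5% and a one-sided test will be used". The next sentence gives 95% intervals for each arm's proportion and adds that "the one-sided 95% confidence interval for the difference in treatment proportion between reparixin and placebo will be produced". Later in 7.5.1, the logistic regression tests the treatment effect at 0.025 and again attaches a one-sided 95% interval to the odds ratio.

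Other places describe the interval for the primary difference without a one-sided qualifier:

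- SAP 3.3: "a 95% confidence interval for the difference of success (failure) rates between the reparixin and placebo groups will be provided". The same paragraph equates a two-sided p-value below 0.05 with a one-sided error rate of 0.025.
- Protocol 9.1: "95% confidence interval for the difference of success (failure) rates between the reparixin and placebo groups will be provided", in the same setting.
- Protocol 9.4.2, beside the same one-sided 2.5% test: "The 95% confidence interval for treatment proportions and for the difference in treatment proportion between reparixin and placebo will be produced".

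SAP 1.2, on changes from protocol, reads "Not pertinent".

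The SAP addendum (3.2.2.3) repeats the one-sided 2.5% test with a one-sided 95% interval for the exploratory HbA1c analysis. The shell for that table prints a lower limit only, in a column headed simply 95% CI, next to two-sided intervals for each arm.

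**The concern.** An interval printed beside a test is normally read as the set of differences the test would not reject. That holds only if the levels match. A one-sided 2.5% test corresponds to a one-sided 97.5% lower limit, which is also the lower end of a two-sided 95% interval. A one-sided 95% limit corresponds to a test at twice the planned level.

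The mismatch always works in one direction: the reported lower limit is more favourable to reparixin than the test allows. The SAP also carries two descriptions of the interval for its main estimate, and the one in the analysis section departs from the protocol without being declared. At stake is how a near-miss on the primary endpoint would look in the study report. Whether the trial succeeds is not at stake.

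**Working it through.** **Inputs.** Test level: one-sided 0.025 (SAP 7.5.1). Interval level: one-sided 95% (SAP 7.5.1). Significance thresholds: 10/44 v 19/44 and 12/52 v 22/52 (SAP 3.3). Success rates by IEQ/kg stratum: placebo 13/23/55%, reparixin 40/55/84% (SAP 3.3). Stratum mix: 34/42/24%, from the recent series in SAP 3.3. Size: 100 patients at 1:1, so 50 per arm.

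**Formulas for the two-arm examples** (unstratified, equal n):

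- Test (Pearson, pooled variance): z = d / √[2p(1−p)/n], where d is the difference and p the pooled proportion.
- Interval (normal approximation, unpooled variance): lower limit = d − k·SE, with SE = √[p₁(1−p₁)/n + p₂(1−p₂)/n]. Here k = 1.645 for one-sided 95% and k = 1.960 for two-sided 95%.

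**Reproducing the plan's thresholds.** 10/44 v 19/44 gives z = 2.041, one-sided p = 0.0206. 12/52 v 22/52 gives z = 2.090, p = 0.0183. Each is the first significant count for its placebo result, as SAP 3.3 implies.

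**Just below the thresholds.** For 10/44 v 18/44:

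- d = 0.1818 and p = 28/88 = 0.3182, so the pooled SE is √(0.3182 × 0.6818 × 2/44) = 0.0993 and z = 1.831, p = 0.0336. The test fails.
- Unpooled SE = √(0.2273 × 0.7727/44 + 0.4091 × 0.5909/44) = 0.0974.
- One-sided 95% lower limit = 0.1818 − 1.645 × 0.0974 = +0.0216.
- Two-sided 95% lower limit = 0.1818 − 1.960 × 0.0974 = −0.0091.

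| Placebo v reparixin | One-sided p | Test at 2.5% | One-sided 95% lower limit | Two-sided 95% lower limit |
|---|---|---|---|---|
| 10/44 v 18/44 | 0.034 | fails | +2.2 points | −0.9 |
| 10/44 v 19/44 | 0.021 | passes | +4.4 | +1.3 |
| 12/52 v 20/52 | 0.045 | fails | +0.7 | −2.1 |
| 12/52 v 21/52 | 0.029 | fails | +2.6 | −0.3 |
| 12/52 v 22/52 | 0.018 | passes | +4.4 | +1.6 |

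The one-sided 95% limit contradicts the test in all three failing rows. The two-sided interval agrees with it in all five.

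**How often, unstratified (exact enumeration, 50 per arm).** Overall rates: placebo 0.34×13 + 0.42×23 + 0.24×55 = 27.28%; reparixin 0.34×40 + 0.42×55 + 0.24×84 = 56.86%.

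| True rates | Test significant | One-sided 95% interval above 0 | Disagree, one-sided 95% | Disagree, two-sided 95% |
|---|---|---|---|---|
| 27.28% in both arms | 2.53% | 5.13% | 2.6% | 0.3% |
| 27.28% v 56.86% | 86.9% | 92.2% | 5.3% | 0.06% |
| 23% v 40% (assumed intermediate effect) | 44.9% | 59.1% | 14.2% | 1.7% |

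Under no effect, the one-sided 95% interval excludes zero about twice as often as the test rejects. The remaining two-sided disagreement arises because the pooled variance exceeds the unpooled by d²/(2n), so this interval is slightly less strict than the test.

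**How often, with the planned CMH test (simulation, 200,000 trials, 50 per arm, strata drawn 34/42/24).** SAP 7.5.1 does not say how the interval for the difference is built, so two estimators were tried.

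| Estimator and measure | One-sided 95%: no effect / planned | Two-sided 95%: no effect / planned |
|---|---|---|
| Mantel-Haenszel difference (Sato variance), total disagreement | 2.9% / 5.0% | 0.3% / 0.9% |
| Crude difference, interval above 0 with a failed test | 3.0% / 4.0% | 1.1% / 1.7% |
| Crude difference, total disagreement | 3.3% / 5.4% | 1.8% / 6.1% |

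**The case against.** The strongest reply is that nothing depends on the interval. Success is decided by the CMH test, the interval is labelled one-sided in the text, and a 95% lower limit is valid at its stated level. All of that is true, and it confines the point to reporting.

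SAP 7.5.1 could also be called the operative text, with SAP 3.3 only repeating sample-size background, and neither SAP 3.3 nor the protocol writes two-sided. That stands in part. The two-sided reading is an inference, though a strong one, from the unqualified 95% and the two-sided 0.05 criterion beside it in SAP 3.3 and protocol 9.1. If 7.5.1 does govern, it departs from protocol 9.4.2 and SAP 1.2 should say so.

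The worked examples use the unstratified test from the sample-size section. Under CMH, 10/44 v 18/44 could pass or fail depending on the strata. This is right: the examples are illustrations, and the simulation covers the planned test.

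The most substantive objection is that changing the level is not a full cure. If the interval is for the crude difference, total disagreement at the planned effect does not fall; it goes from 5.4% to 6.1%, because more trials then have a significant test with an interval that includes zero. The fault raised here, an interval above zero after a failed test, does fall, from 4.0% to 1.7%. The stratified residual also depends on the variance formula: fixed strata of 17/21/12 per arm and a simple unpooled variance leave 0.6% and 1.6% for that same fault, against total disagreement of 0.3% and 0.9% with Sato variance.

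Finally, the addendum's section on the primary variable and the shell for the primary table were not available for this check, so nothing is claimed about how that table is headed.

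**Conclusion.** The concern holds. SAP 7.5.1 pairs a one-sided 2.5% test with an interval at the one-sided 5% level, for both the primary difference and the logistic odds ratio. This conflicts with SAP 3.3 and with protocol 9.1 and 9.4.2, and SAP 1.2 does not declare it.

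The consequence is limited to reporting. The decision, type I error, power and fixed sequence are unchanged. A contradictory display would occur in roughly 3% of trials under no effect and 4% to 5% at the planned effect. It would be more frequent at effects in between: 14.2% at 23% v 40%, unstratified. These figures assume 50 per arm, the historical 34/42/24 stratum mix, the plan's stratum rates and normal-approximation intervals. The addendum's HbA1c analysis has the same mismatch but matters less because it is exploratory. The point merits correction because it concerns the effect estimate for the primary endpoint and takes only a few words to put right.

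**What to change.** 1. In SAP 7.5.1, specify a two-sided 95% interval, or equivalently a one-sided 97.5% lower limit, for the difference in proportions and for the logistic odds ratio. State the same interval in SAP 3.3. The SAP then agrees with the protocol on this point and SAP 1.2 needs no entry for it.
2. At lower priority, make the same change in addendum 3.2.2.3 and its table shell, with a column heading that matches what is printed.
3. Optionally, name the interval method. A Mantel-Haenszel stratified risk difference brings the interval much closer to the CMH test, though it does not remove every disagreement. It is worth doing at the same time, because with a crude difference the change of level alone does not reduce total disagreement at the planned effect.

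The cost is SAP and shell wording before database lock, with no new data. The only downside for the sponsor is a less favourable lower limit: in the 10/44 v 18/44 example it moves from +2.2 to −0.9, about 3 points.

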### 3. OVERALL STUDY DESIGN AND PLAN DESCRIPTION

#### 3.1. STUDY DESIGN

*The following paragraph [protocol, page 20] has been changed from:*

Recruitment will be competitive among the study sites, until the planned number of patients is enrolled. Competitive recruitment has been chosen to increase the speed of recruitment and to account for any difference in transplant rate among study sites. Each centre will enroll patients as rapidly as possible, up to a maximum of 40 patients (as per the randomization list).

*To:*

Recruitment will be competitive among the study sites, until the planned number of patients is enrolled. Competitive recruitment has been chosen to increase the speed of recruitment and to account for any difference in transplant rate among study sites. Each centre will enroll patients as rapidly as possible, up to a maximum of 40 patients (as per the randomization list). A maximum of 48 patients is allowed for the site of the Primary Investigator.

**Reason:** The study design has been changed considering current patient enrollment status. Specifically, since the first patient randomized to the trial back in February 2014, recruitment is extending considerably longer than originally expected. To date, 86 patients have received TP-IAT, out of 89 randomized. New sites in addition to those originally involved have joined the trial with Cincinnati and UCSF having been initiated early in 2016. Despite this continuous effort, overall enrollment rate across the 9 participating sites is lower than predicted, mainly due to the very rare condition of the TP-IAT procedure, coupled with a non-homogeneous distribution of this procedure across the US states/sites. In particular, enrollment rate has significantly decrease since the site of the Primary Investigator (UMN) has reached the cap of 40 patients (out of 89 randomized to date) allowed at a single site as per protocol. The high enrollment rate of this site actually reflects the high volume of TP-IAT procedures specific for Minnesota. Therefore, considering the importance of:

- maintaining study continuity;
- achieving a timely completion of the trial in order to avoid “dilution” over time of data obtained and potential bias on data reproducibility;
- distribution of TP-IAT procedures across different US sites;

the study design has been changed to allow enrollment at the site of the Primary Investigator up to a total of 48 patients.

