### **3. OVERALL STUDY DESIGN AND PLAN DESCRIPTION**

#### **3.1. STUDY DESIGN**

The study will be a phase 2/3, multicenter (US), randomized, double-blind, placebo-controlled, parallel assignment pilot study.

The goal of this study is to reach a total of 100 adult patients who are randomized and receive IAT after total or completion pancreatectomy. Patients will be randomly (1:1) assigned to receive either reparixin [continuous i.v. infusion for 7 days (168hrs)], or matched placebo (control group), starting approximately 12hrs before islet infusion. The two groups will be balanced within each centre. All patients who are randomized and receive the Investigational Product (either reparixin or placebo) will be included in the ITT analysis. Patients will be in the ITT analysis whether or not they receive IAT, because exclusions cannot be made for events occurring after randomization that could be influenced by the randomized assignment.

Recruitment will be competitive among the study sites, until the planned number of patients is enrolled. Competitive recruitment has been chosen to increase the speed of recruitment and to account for any difference in transplant rate among study sites. Each centre will enroll patients as rapidly as possible, up to a maximum of 40 patients (as per the randomization list). A maximum of 48 patients is allowed for the site of the Primary Investigator. Each patient will be involved in the study for 7 day hospital stay during pancreatectomy followed by islet transplantation, for all required measurements up to hospital discharge and for 2 post-transplant visits scheduled @ day  $75\pm 14$  and  $365\pm 14$  after the transplant.

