The treatment effect ( $\beta_{\text{treatment}}$ ) will be declared significantly greater than 0 at the 0.025  $\alpha$ -level. A model parameter estimate and the corresponding standard error, p-value, and odds ratio with a one-sided 95% confidence interval will be presented for the treatment effect.

The logistic regression sensitivity analysis will also be performed for the ITT population, dropping from the analysis any site with >20% of subjects not having the primary endpoint recorded, using the same approach used for the sensitivity analysis of the primary endpoint.

As further sensitivity analysis, the primary endpoint analysis and the corresponding logistic regression analysis will be repeated including Site 01 only, which is the largest site with the greatest number of patients receiving IAT, having possibly the best treatment balance, having a high rate of primary endpoint data capture, and also being the site with the highest experience in the field and thus transplanting patients under highly reproducible surgical and clinical conditions. When performing the logistic regression analysis, site will no longer be considered a covariate in the model. The intent of these analyses is to examine the sensitivity of the primary analysis to the low enrollment/treatment balance, lesser experience level, and lower rates of retention which may be present at the other sites.

For both the primary and sensitivity analyses, patients who die or who discontinue before the primary endpoint assessment at Day 365  $\pm$  14 days after IAT, or those who reach the Day 365 visit but have no primary endpoint assessment, will be treated as primary endpoint failures.

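### If the design effect is true, the site-adjusted logistic sensitivity model will overstate the treatment odds ratio by roughly 17–27%, and its lower confidence bound will cover too little

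*SAP*

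**What the plan says.** SAP 7.5.1 (Primary Variable, under Primary Analysis) makes the primary test a Cochran-Mantel-Haenszel test stratified by IEQ/kg, without site. It then adds a logistic regression with treatment, three-level IEQ/kg and site as covariates. Site is categorical: "the analysis variables for site will be coded such that the reference site is Site 1". On the interaction: "The treatment-by-site interaction will be examined, and if not significant at the 0.10" level, it is removed. The site main effects stay. Treatment is tested one-sided at 0.025, and the output is specified as "A model parameter estimate and the corresponding standard error, p-value, and odds ratio" with a one-sided 95% confidence interval.

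The model is repeated after dropping sites with more than 20% missing primary data. The SAP table list also gives it for the per-protocol population. A further repeat uses "Site 01 only, which is the largest site with the greatest number of patients receiving IAT"; there the SAP removes site from the model. Patients without a primary assessment count as failures, so the sample is not reduced.

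The protocol amendment to Section 3.1 says that "overall enrollment rate across the 9 participating sites is lower than predicted", with 40 of 89 randomized patients at one site. Protocol 3.1 adds: "A maximum of 48 patients is allowed for the site of the Primary Investigator". SAP 3.3 says "it is planned to enroll 100 patients in this trial who receive IAT".

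**The concern.** Eight of the nine sites share a little over half the patients, and each needs its own intercept. When many intercepts are each estimated from a handful of patients, maximum likelihood follows the data too closely and the treatment log odds ratio drifts away from zero.

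The SAP text available names no penalised, exact or conditional method for this model and no rule for pooling small sites. The addendum has a sparse-data fallback (Section 3.2.2.2), but only for the insulin-requirement model.

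At stake is the size of a reported effect. If reparixin works as well as planned, Tables 14.2.2.1, 14.2.2.1.A and 14.2.2.2 would tend to show a site-adjusted odds ratio above 5 where the truth is near 4.3. A reader could take that as extra support for the primary result.

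**Working it through.** **Plan's own figures.**
- Odds ratios: (0.55/0.45)/(0.23/0.77) = 4.09; (0.40/0.60)/(0.13/0.87) = 4.46; (0.84/0.16)/(0.55/0.45) = 4.30. These agree with SAP 3.3, so a common value of about 4.3 represents the design effect.
- Power at 44 per arm, 23% versus 55%: 88.2% (pooled variance), 90.3% (unpooled), 88.8% (exact enumeration of the Pearson test). The stated 90%, or 87–90% allowing for discreteness, is reproduced.

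**Size of the model.**
- Control rates from SAP 3.3: "<2500 IEQ/kg: 13% insulin independence", then 23% and 55%. Stratum shares in the recent series: 34%, 42%, 24%.
- Control success: 0.34×0.13 + 0.42×0.23 + 0.24×0.55 = 0.273.
- Reparixin success: 0.34×0.40 + 0.42×0.55 + 0.24×0.84 = 0.569.
- Average (0.273 + 0.569)/2 = 0.421, so about 42 successes in 100 patients.
- Covariate terms: 1 treatment + 2 IEQ/kg + 8 site = 11, plus an intercept. 42/11 = 3.8 successes per term.
- With 48 patients at the largest site, 100 − 48 = 52 to 105 − 48 = 57 remain for eight sites: 6.5 to 7.1 patients each, or about 6.5 × 0.421 = 2.7 successes at a typical small site.

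**Simulation.** Ordinary maximum likelihood, no interaction, blocks of 4 within site, rates and shares as above, true odds ratio 4.3. Site sizes are not in the documents. They were assumed: Site 1 = 48, the other eight from even (6–8 each) to very skewed (24 down to 2), total 100–105. Site effects had a standard deviation (SD) of 0, 0.5 or 1.0 on the logit scale. Each cell used 5,000 trials and shows the median fitted odds ratio, exp(median log odds ratio), with its excess over 4.3.

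| Site sizes | SD 0 | SD 0.5 | SD 1.0 |
|---|---|---|---|
| Even | 5.31 (+24%) | 5.42 (+26%) | 5.41 (+26%) |
| Skewed | 5.21 (+21%) | 5.22 (+21%) | 5.28 (+23%) |
| Very skewed | 5.19 (+21%) | 5.19 (+21%) | 5.31 (+24%) |

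The Monte Carlo standard error of the mean log odds ratio is 0.008–0.009. Over all runs with Site 1 at 48, the median excess was 17–27%. With Site 1 at 40 it was +29%; with only six contributing sites, +18%. The lower one-sided 95% bound covered 89–92%.

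**Dependence on the true effect.**

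| True odds ratio | Median excess |
|---|---|
| 4.2–4.3 | 17–27% |
| 3.0 | 17% |
| 2.0 | 8–13% |
| 1.5 | 5–7% |
| 1.0 | about 0 |

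**Alternatives at true 4.3, skewed sizes unless noted.**
- Site omitted: +5% median, so most of the excess comes from the site terms.
- Small sites pooled, giving three site groups (48, 28 and 29 patients): +9%.
- Firth's penalty with all nine sites: −3% median, geometric mean on target.
- Conditional logistic regression stratified by site, at true 4.2: median 4.2–4.6, or 0 to +10% (4.6/4.2 = 1.10).

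**False positives at odds ratio 1, nominal 2.5%.** Wald tests gave 2.5–3.0% and likelihood-ratio tests 3.0–3.3%. Runs in which the test type was not recorded gave 2.5–3.4%, and one smaller run 2.9–3.9% (Monte Carlo standard error about 0.4 points). Firth gave 1.9–2.2%.

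**The case against.** **The consequence is limited.** The primary inference does not use this model, and the SAP labels its tables as sensitivity analyses. The shift in log odds ratio is about 0.18–0.24, against a standard error of about 0.53, so less than half a standard error. This stands. It limits the importance of the point but does not remove the bias or the under-coverage.

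**The inputs are uncertain.** Site sizes are assumed, nine is a mid-trial count, and maximum likelihood is inferred because the SAP says only logistic regression. The addendum's Section 3.2.1 (Primary Variable) was not in the text available, so it may say something relevant. All of this stands. The bias nevertheless appeared under every site-size pattern tried, including six sites.

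**Stronger readings that a reader might infer:**
- *The odds ratio is overstated by a fifth whatever the truth.* It is not. The excess grows with the effect and is nil if the drug does nothing.
- *The 0.025-level test is anti-conservative.* Reporting an estimate, standard error and p-value most naturally implies a Wald test, whose rejection rate was close to nominal.
- *Sites with all successes or all failures break the analysis.* They are likely, and their site coefficients are infinite. But such a site contributes nothing to the treatment likelihood, so the treatment odds ratio stays finite. Conditional logistic regression discards the same sites, and the SAP asks only for the treatment effect to be reported.

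**Conclusion.** The point holds as a bias in a reported estimate, conditional on a sizeable true effect. At the design odds ratio of about 4.2–4.3, the site-adjusted model gives a median odds ratio roughly 17–27% too high, and a lower one-sided 95% bound that covers about 89–92%. At a true odds ratio of 2 the excess is about 8–13%; at 1 there is none, and the false-positive rate is not materially inflated.

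It affects the site-adjusted model in the ITT population, its repeat without high-missing sites, and its per-protocol version. A reader might infer that the primary result is compromised. It is not, because the Cochran-Mantel-Haenszel test has no site term, and neither does the Site 01-only logistic model.

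The figures assume ordinary maximum likelihood, nine contributing sites, the largest site (taken to be Site 1) at 48 patients, the plan's rates and shares, and the interaction dropped. The roughly five patients expected not to receive IAT, who have no infused IEQ/kg, were not modelled separately.

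**What to change.** In SAP 7.5.1, prespecify Firth's penalised likelihood with profile-likelihood confidence intervals for the site-adjusted logistic model, keeping treatment, IEQ/kg and site as covariates. Apply it also to the repeat that drops sites with more than 20% missing data and to the per-protocol version. Conditional logistic regression stratified by site is an acceptable alternative. Settle the choice before unblinding.

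This is one option in the logistic procedure, needs no new data, and leaves the primary analysis unchanged. The cost is a smaller reported odds ratio and a slightly conservative test, about 2% for a nominal 2.5%. In the skewed-site runs, rejection at odds ratio 4.3 was about 88% with Firth, against 91–92% with maximum likelihood at site SD 0 or 0.5.
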